## 13.3 Analysis of Correlative Endpoint

We anticipate that approximately 75% of patients will consent to have prostate samples removed at the time of the fiducial placement. We expect to detect tumor from samples from at least half of these patients. Therefore we expect that we will have conservatively ~24 patients that have samples that are evaluable. Nuclear expression grade will be tabulated. This unique resource will serve as a pilot to help in the understanding of the mechanism of enzalutamide action when the pattern of AR expression is compared to pre-treatment biopsy samples and samples from other patient tumors.

## **15. APPENDICES**

**Appendix A: PROMIS Sleep Survey**

**Appendix B: Pittsburg Sleep Quality Index**

**Appendix C: EPIC-26**

**Appendix D: Eastern Cooperative Oncology Group Performance Status**

**Appendix E: Research Labs**

**Appendix F: Drugs to be used with caution or avoided**

**Appendix G: Charts to calculate body fat %**

**Appendix H: Pill Diary**

CONFIDENTIAL

This document is confidential. Do not disclose or use except as authorized.

**Appendix A:**

Investigator Format © 2008-2012 PROMIS Health Organization and PROMIS Cooperative Group Page 1 of 1

PROMIS Item Bank v1.0 – Pain Interference – Short Form 8a

**Pain Interference – Short Form 8a****Please respond to each question or statement by marking one box per row.****In the past 7 days...**

		Not at all	A little bit	Somewhat	Quite a bit	Very much
PAININ9 1	How much did pain interfere with your day to day activities? .....	 1	 2	 3	 4	 5
PAININ22 2	How much did pain interfere with work around the home?.....	 1	 2	 3	 4	 5
PAININ31 3	How much did pain interfere with your ability to participate in social activities?	 1	 2	 3	 4	 5
PAININ34 4	How much did pain interfere with your household chores?.....	 1	 2	 3	 4	 5
PAININ12 5	How much did pain interfere with the things you usually do for fun? .....	 1	 2	 3	 4	 5
PAININ36 6	How much did pain interfere with your enjoyment of social activities?.....	 1	 2	 3	 4	 5
PAININ3 7	How much did pain interfere with your enjoyment of life? .....	 1	 2	 3	 4	 5
PAININ13 8	How much did pain interfere with your family life? .....	 1	 2	 3	 4	 5

SAMP

CONFIDENTIAL

This document is confidential. Do not disclose or use except as authorized.

Version 13.0 Protocol Version Date: 1/09/2015

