### 1.3 Secondary Objectives

1. Assessment of the effect of treatment on health-related quality of life including fatigue, sleep quality, as well as urinary, bowel, sexual and hormonal functioning.
2. Assessment of the effect of treatment on serum sex hormones including androgens and estrogens.
3. Assessment of the effect of treatment on body fat distribution and muscle mass.
4. Assessment of safety and tolerability according to adverse event reporting during the trial.
5. Assessment of the effect of treatment on bone metabolism.

CONFIDENTIAL

This document is confidential. Do not disclose or use except as authorized.

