## 8.0 STUDY CALENDAR

	Screening (4 week period)	Baseline (Day One Cycle 1) 5+/- 3 day	At fiducial placement (3-7 weeks) (Study) (+/- 3 day)	Cycle 2, Day One (+/- 3 day)	Cycle 3, Day One (+/- 3 day)	Cycle 4, Day One (+/- 3 day)	Cycle 5, Day One (+/- 3 day)	Cycle 6, Day One (+/- 3 day)	End of cycle 6 (+/- 3 day)	3  months after completion of cycle 6
Hx/PE	X	X		X	X	X	X	X	X	X
Vital signs	X	X		X	X	X	X	X	X	X
Height/weight 		X		X	X	X	x	x	x	
CBC with diff	X	X		X	X	X	X	X	X	X
Chemistry/LFTs 	X	X		X	X	X	X	X	X	X
Bone Metabolism markers 		X							X	X
PSA	X	X		X	X	X	X	X	X	X
Hormonal measurements 	X 11	X					X		X	
Anthropomorphic measurements  and waist circumference		X							X	
Prostate tissue samples (optional)			X							
Q of L assessment 		X			X		X		X	X
Dispense med/Pill diary		X		X	X	X	X	X	X 7	
Adverse event and con med		X		X	X	X	X	X	X	
EBRT				X 8	X 					
Sign Informed Consent	X									
EKG	X									
Assessment of breast enlargement 		X		*	*	X	*	*	X	

- 1 -bone specific alk phos, serum C-teleopeptide, serum N terminal propeptide of type I collagen (fasting)
- 2- DHEA sulfate, estrogen (estradiol), free testosterone, total testosterone, estrone, androstenedione. These should be done while fasting.
- 3 -Triceps skin fold, biceps (mid-upper arm circumference), shoulder blade and waist. Height will only be necessary at the baseline visit.
- 4- EPIC-26, PROMIS, PSQI
- 5 -Any time between Day -7 to day 1
- 6- +/- 7 days
- 7- Collect pill diary and unused drug
- 8 - EBRT 7-10 weeks after initiating enzalutamide. This could fall on cycle 2 or 3.
- 9 -Chemistries includes: creatinine, BUN, potassium, sodium, bicarbonate LFT's include AST, ALT, total bilirubin and alkaline phosphatase.
- 10- Assessment will be done with calipers. The maximum diameter of the larger breast (if there is asymmetry) at Baseline (Day One Cycle 1), Cycle 4/day 1, End of Cycle 6 and assess it according to these parameters: grade 1 (<=2cm), grade 2 (>2-<=4cm), grade 3 (>4-6cm), and grade 4 (>6cm).
- 11- At screening visit, the only hormonal test required is total testosterone which will not require morning collection or fasting.\* We will ask you to answer a yes or no about breast tenderness and/or enlargement at every study visit.

CONFIDENTIAL

This document is confidential. Do not disclose or use except as authorized.

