#### 9.2.2. Health-Related Quality of Life

HRQoL will be assessed at baseline, at the beginning of cycles 3 day 1, cycle 5 day 1, end of cycle 6 and 3 months after completion of study.

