#### Patient-Reported Outcome Measurement Information System (PROMIS)-Fatigue Short Form

PROMIS was developed as part of the NIH Roadmap Initiative, focused on developing a publicly available resource of standardized, accurate, and efficient PRO measures of symptoms, distress, and functioning. Two content domains of fatigue, experience and impact, were identified by a panel of experts. An item pool of 58 fatigue experience and 54 fatigue impact items were developed. The psychometric properties of these items were evaluated in a sample of 450 individuals from the general US population using classical test theory indices, monotonicity, and scalability. The expert panel selected the 10 best items in each domain. These 20 items were presented to a panel of clinical experts. Only one item was dropped because of redundancy. A fatigue short-form measure of 7 items was created using items selected for consistency in the response scale, broad coverage across the fatigue continuum (i.e., high to low), and good precision of measurement (discrimination function).

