## 13.2 Analysis of Secondary Endpoints

### 13.2.1 Health related quality of life

The primary HRQoL aim is to assess the change from baseline to the end of cycle 6 in the vitality or hormonal function score as well as the sexuality score on the EPIC-26 questionnaire. It is anticipated approximately 75% of patients will have both scores for each domain. A one-sample t-test will be used to assess the overall change in score. To be considered a clinically meaningful difference will be defined as half historical standard deviation for the specific domain. Given 48 evaluable patients, there is 80% power to detect a 0.41 change in the hormonal domain score of the EPIC-26 assuming 2-sided 5% alpha. Results in this study will be evaluated in the context of past research by Sanda et al showing patients that received radiotherapy with non-hormonal therapy had a score on the vitality or hormonal function domain of approximately 80 and a score on the sexuality domain of 26.

Descriptive statistics at each time point and changes over time will be provided for each of the EPIC-26 domains as well as for the PROMIS-Fatigue and PSQ1. Mixed models will be used to explore the impact of time on quality of life adjusting for prognostic baseline factors.

13.2.2 Safety and Tolerability: We will monitor toxicities experienced by all treated patients. Frequency and severity of worst grade 3 or higher treatment-related AEs by type will be reported along with the incidence of overall grade 3 or higher treatment-related AEs. With 71 treated patients, the maximum width of a 90% CI for a given toxicity is 21%. The probability of observing one rare severe toxicity (true rate=5%) is 97%. Tolerability endpoints include the number of dose reductions and treatment interruptions as well as the number of patients that discontinue treatment due to AEs. The safety summary will include clinical laboratory, ECG and vital signs data.

13.2.3 Hormone Levels: Descriptive statistics at each time point and changes over time will be provided for all hormone measures. Paired t-tests and two-sample t-tests (or non-parametric equivalents) will be used to assess significance of change over 6 cycles of treatment in hormone levels for the overall cohort and by status on primary clinical endpoint (yes or no achieving PSA level  $\leq 0.20$  ng/ml at the end of 6 cycles of treatment with enzalutamide and EBRT).

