**during the last 4 weeks?**

No problem.....	1
Very small problem.....	2
Small problem.....	3
Moderate problem.....	4
Big problem.....	5

(Circle one number)

68/

13. How big a problem **during the last 4 weeks**, if any, has each of the following been for you?  
(Circle one number on each line)

	No Problem	Very Small Problem	Small Problem	Moderate Problem	Big Problem	
a. Hot flashes.....	0	1	2	3	4	74/
b. Breast tenderness/enlargement..	0	1	2	3	4	75/
c. Feeling depressed.....	0	1	2	3	4	77/
d. Lack of energy.....	0	1	2	3	4	78/
e. Change in body weight.....	0	1	2	3	4	79/

THANK YOU VERY MUCH!!

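### Appendix A prints a pain questionnaire under a sleep title, while Sections 9.2.2 and 13.2.1 call for PROMIS-Fatigue; if sites use the printed form, no fatigue score is obtained

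*Combined protocol and SAP*

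**What the plan says.** The first secondary objective (Section 1.3) covers "health-related quality of life including fatigue, sleep quality" and several functional domains. In Section 9.2.2 the only PROMIS measure described is the Fatigue Short Form: "A fatigue short-form measure of 7 items was created using items selected for consistency in the response scale". Section 13.2.1 plans descriptive statistics at each time point and over time for the "EPIC-26 domains as well as for the PROMIS-Fatigue and PSQ1" (the last name evidently meaning the PSQI), and mixed models to explore the effect of time on quality of life.

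The schedule comes from Section 9.2.2 ("HRQoL will be assessed at baseline, at the beginning of cycles 3 day 1", then cycle 5 day 1, end of cycle 6 and three months after completion) and from the calendar in Section 8, whose footnote 4 lists the instruments as "4- EPIC-26, PROMIS, PSQI" without naming the PROMIS domain.

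The list in Section 15 gives "Appendix A: PROMIS Sleep Survey". The page under the Appendix A heading is headed Pain Interference, Short Form 8a. Its first item is "How much did pain interfere with your day to day activities", and the other seven also ask how far pain interfered with some part of life.

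**The concern.** The protocol attaches three domains to one instrument: fatigue in the body text, sleep in the list of appendices, and pain on the printed form. Only the first matches an objective or an analysis. Sleep is already covered by the PSQI in Appendix B, and pain interference appears in no objective, endpoint or analysis.

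PROMIS-Fatigue is the only dedicated patient-reported fatigue scale in the plan. Section 2.1.1 reports fatigue as the most frequent adverse event in the dose-escalation study, and Section 2.3 lists it among the effects of LH-RH agonists that enzalutamide might avoid. If a site copies the protocol's own form, it collects answers that cannot be scored as fatigue. A baseline missed in this way cannot be recovered later. Several hospitals take part, so different sites could also be using different forms.

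**Working it through.** No figure in the plan rests on the PROMIS instrument, so the check is mainly a comparison of text.

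**Which domain each place names**

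| Place | Domain | Items |
|---|---|---|
| Section 1.3, objective 1 | Fatigue (no instrument named) | – |
| Section 9.2.2 | Fatigue | 7 |
| Section 13.2.1 | Fatigue | – |
| Section 8, footnote 4 | Not stated | – |
| Section 15, list of appendices | Sleep | – |
| Appendix A, printed form | Pain interference | 8 |

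The printed form differs from the specified one in title, length (8 against 7) and content: 8 of 8 items are about pain and 0 of 8 about fatigue or sleep. It is legible and complete, marked page 1 of 1, so the mismatch is not a broken table. No fatigue form appears in any other appendix.

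**What else could stand in for the score**

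- EPIC-26 item 13d ("Lack of energy") is one item of the vitality/hormonal domain.
- PSQI questions 8 and 9 feed the daytime-dysfunction component.
- Fatigue is CTCAE-graded as an adverse event, but the by-type summary in Section 13.2.2 covers only treatment-related events of grade 3 or higher.

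Each touches on fatigue. None yields a PROMIS-Fatigue score.

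**Size if the printed form is in use at every site**

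Inputs: 71 enrolled and 64 evaluable (Section 13.1); five quality-of-life time points (Sections 8 and 9.2.2); 75% of patients expected to have both scores (Section 13.2.1, stated for the EPIC-26 domains).

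- Scheduled administrations, all enrolled: 71 × 5 = 355.
- Scheduled administrations, evaluable target: 64 × 5 = 320.
- Patients who would have given a fatigue change from baseline to end of cycle 6, assuming the EPIC-26 completion rate carries over to PROMIS: 0.75 × 64 = 48. With full completion this would be 64. With the pain form it is 0.

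The first two are ceilings that assume full retention. If sites already use the fatigue form, the loss is 0.

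**What does not depend on PROMIS**

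- The primary rule of 44 or more successes in 64 gives an exact binomial α of 0.0953 at 60% and β of 0.0993 at 75%, against the stated 0.095 and 0.099.
- The EPIC-26 power statement (48 patients, a change of 0.41 read in standard-deviation units, two-sided 5%) gives power 0.794, against the stated 80%.

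Neither calculation uses PROMIS.

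**The case against.** The strongest reply is that the operative text is consistent. The objective names fatigue, Section 9.2.2 describes only the fatigue form, and Section 13.2.1 analyses only that form. Read with Section 9.2.2, footnote 4 most naturally means fatigue too. No sentence in the body sends sites to Appendix A, whereas Appendices D, F and G are each called from the text. The printed page also carries a cut-off mark reading SAMP, which suggests a sample copy and not the form in use. On this view the error is confined to an appendix, and the counts above measure a possibility that nothing in the documents confirms.

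Much of this stands. The intended instrument is clear to a careful reader, and the data loss is conditional. The counts are bounds and not estimates. Section 13.2.1 names PROMIS-Fatigue only for descriptive statistics; applying the exploratory mixed model to it is the natural reading but is not stated. PROMIS-Fatigue has no hypothesis test, power statement or decision rule. Section 10.2 has all adverse events recorded, so milder fatigue would still be on the case report forms.

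It does not remove the point. The only PROMIS form the protocol supplies cannot produce the planned score, and a sample copy of the wrong instrument is still the wrong instrument. Nothing in the documents shows that sites obtained the right form elsewhere.

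**Conclusion.** The concern holds as a contradiction in the current text and should be fixed. That Appendix A is the wrong form, under a title that fits neither the form nor the plan, is certain. Whether data were lost is unknown: the effect runs from none, if sites give the fatigue form, to no PROMIS-Fatigue score at any of the five time points, if all give the printed one. The upper end assumes universal use of the printed form, and the figure of 48 lost change scores also assumes that the EPIC-26 completion rate applies to PROMIS. The damage would fall on one named component of a secondary objective, analysed descriptively. The conclusions on PSA and on the EPIC-26 hormonal and sexuality scores do not depend on it.

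**What to change.** - Replace the page in Appendix A with the 7-item PROMIS-Fatigue Short Form described in Section 9.2.2.
- Correct the Appendix A title in the Section 15 list, and name the form and its 7 items in footnote 4 of the calendar.
- Ask each site which form has been given, and record the answer before analysis.
- If the fatigue form was used, leave Section 13.2.1 as it is. If the pain form was used, report those responses as pain interference, do not score them as fatigue, and restrict the PROMIS-Fatigue change analysis to patients with a fatigue-form baseline. If use was mixed, also report how many patients had each form at each time point.

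The cost is one appendix page, one title, one footnote and one query to sites, carried in an amendment that needs IRB approval under Section 12.1. No visits or time points are added.

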**Appendix B:**

**PITTSBURGH SLEEP QUALITY INDEX**

---

**INSTRUCTIONS:**

The following questions relate to your usual sleep habits during the past month only. Your answers should indicate the most accurate reply for the majority of days and nights in the past month.

Please answer all questions.

---

1. During the past month, what time have you usually gone to bed at night?

BED TIME \_\_\_\_\_

2. During the past month, how long (in minutes) has it usually taken you to fall asleep each night?

NUMBER OF MINUTES \_\_\_\_\_

3. During the past month, what time have you usually gotten up in the morning?

GETTING UP TIME \_\_\_\_\_

4. During the past month, how many hours of actual sleep did you get at night? (This may be different than the number of hours you spent in bed.)

HOURS OF SLEEP PER NIGHT \_\_\_\_\_

*For each of the remaining questions, check the one best response. Please answer all questions.*

5. During the past month, how often have you had trouble sleeping because you . . .

- a) Cannot get to sleep within 30 minutes

Not during the past month _____	Less than once a week _____	Once or twice a week _____	Three or more times a week _____
---------------------------------	-----------------------------	----------------------------	----------------------------------

- b) Wake up in the middle of the night or early morning

Not during the past month _____	Less than once a week _____	Once or twice a week _____	Three or more times a week _____
---------------------------------	-----------------------------	----------------------------	----------------------------------

- c) Have to get up to use the bathroom

Not during the past month _____	Less than once a week _____	Once or twice a week _____	Three or more times a week _____
---------------------------------	-----------------------------	----------------------------	----------------------------------

Version 13.0 Protocol Version Date: 1/09/2015

d) Cannot breathe comfortably

Not during the past month \_\_\_\_\_ Less than once a week \_\_\_\_\_ Once or twice a week \_\_\_\_\_ Three or more times a week \_\_\_\_\_

e) Cough or snore loudly

Not during the past month \_\_\_\_\_ Less than once a week \_\_\_\_\_ Once or twice a week \_\_\_\_\_ Three or more times a week \_\_\_\_\_

f) Feel too cold

Not during the past month \_\_\_\_\_ Less than once a week \_\_\_\_\_ Once or twice a week \_\_\_\_\_ Three or more times a week \_\_\_\_\_

g) Feel too hot

Not during the past month \_\_\_\_\_ Less than once a week \_\_\_\_\_ Once or twice a week \_\_\_\_\_ Three or more times a week \_\_\_\_\_

h) Had bad dreams

Not during the past month \_\_\_\_\_ Less than once a week \_\_\_\_\_ Once or twice a week \_\_\_\_\_ Three or more times a week \_\_\_\_\_

i) Have pain

Not during the past month \_\_\_\_\_ Less than once a week \_\_\_\_\_ Once or twice a week \_\_\_\_\_ Three or more times a week \_\_\_\_\_

j) Other reason(s), please describe \_\_\_\_\_  
\_\_\_\_\_

How often during the past month have you had trouble sleeping because of this?

Not during the past month \_\_\_\_\_ Less than once a week \_\_\_\_\_ Once or twice a week \_\_\_\_\_ Three or more times a week \_\_\_\_\_

6. During the past month, how would you rate your sleep quality overall?

Very good \_\_\_\_\_

Fairly good \_\_\_\_\_

Fairly bad \_\_\_\_\_

Very bad \_\_\_\_\_

7. During the past month, how often have you taken medicine to help you sleep (prescribed or "over the counter")?

Not during the past month	Less than once a week	Once or twice a week	Three or more times a week
---------------------------	-----------------------	----------------------	----------------------------

8. During the past month, how often have you had trouble staying awake while driving, eating meals, or engaging in social activity?

Not during the past month	Less than once a week	Once or twice a week	Three or more times a week
---------------------------	-----------------------	----------------------	----------------------------

9. During the past month, how much of a problem has it been for you to keep up enough enthusiasm to get things done?

No problem at all \_\_\_\_\_

Only a very slight problem \_\_\_\_\_

Somewhat of a problem \_\_\_\_\_

A very big problem \_\_\_\_\_

10. Do you have a bed partner or room mate?

No bed partner or room mate \_\_\_\_\_

Partner/room mate in other room \_\_\_\_\_

Partner in same room, but not same bed \_\_\_\_\_

Partner in same bed \_\_\_\_\_

If you have a room mate or bed partner, ask him/her how often in the past month you have had . . .

a) Loud snoring

Not during the past month	Less than once a week	Once or twice a week	Three or more times a week
---------------------------	-----------------------	----------------------	----------------------------

b) Long pauses between breaths while asleep

Not during the past month	Less than once a week	Once or twice a week	Three or more times a week
---------------------------	-----------------------	----------------------	----------------------------

c) Legs twitching or jerking while you sleep

Not during the past month	Less than once a week	Once or twice a week	Three or more times a week
---------------------------	-----------------------	----------------------	----------------------------

d) Episodes of disorientation or confusion during sleep

Not during the past month \_\_\_\_\_ Less than once a week \_\_\_\_\_ Once or twice a week \_\_\_\_\_ Three or more times a week \_\_\_\_\_

e) Other restlessness while you sleep; please describe \_\_\_\_\_

Not during the past month \_\_\_\_\_ Less than once a week \_\_\_\_\_ Once or twice a week \_\_\_\_\_ Three or more times a week \_\_\_\_\_

© 1989, University of Pittsburgh. All rights reserved. Developed by Buysse,D.J., Reynolds,C.F., Monk,T.H., Berman,S.R., and Kupfer,D.J. of the University of Pittsburgh using National Institute of Mental Health Funding. Buysse DJ, Reynolds CF, Monk TH, Berman SR, Kupfer DJ: Psychiatry Research, 28:193-213, 1989.

<https://www.sleep.pitt.edu/instruments/>

---

**SCORING INSTRUCTIONS FOR THE PITTSBURGH SLEEP QUALITY INDEX:**

The Pittsburgh Sleep Quality Index (PSQI) contains 19 self-rated questions and 5 questions rated by the bed partner or roommate (if one is available). Only self-rated questions are included in the scoring. The 19 self-rated items are combined to form seven "component" scores, each of which has a range of 0-3 points. In all cases, a score of "0" indicates no difficulty, while a score of "3" indicates severe difficulty. The seven component scores are then added to yield one "global" score, with a range of 0-21 points, "0" indicating no difficulty and "21" indicating severe difficulties in all areas.

Scoring proceeds as follows:

---

